## 6.2 Safety Evaluations

Safety will be assessed by evaluations of the following variables:

- Adverse events, including GI symptoms
- 12-lead ECGs
- Vital signs, including changes in body weight and BMI
- Laboratory safety data, including electrolyte balance
- Antibodies to teduglutide and ECP. Samples for antibody analysis will be drawn at the start of treatment and at the EOT visit (prior to the administration of teduglutide and at least 14 hours after the previous dose). A 6-month follow-up is planned for any subjects testing positive for teduglutide-specific antibodies following the last dose of study drug.
- Changes in urine output (48-hour oral fluid intake/urine output)
- Abdominal ultrasound
- Upper GI contrast series with small bowel follow-through
- Colonoscopy/sigmoidoscopy of remnant colon
- Physical examinations

### 6.2.1 Adverse Events

During the study, the investigator is responsible for the detection and documentation of any AE or SAE, as defined in this protocol.

### 6.2.1.1 Adverse Event Definition

An AE is defined as any untoward medical occurrence in a subject or clinical investigation subject administered a pharmaceutical/medicinal product. An AE does not necessarily have to have a causal relationship with this treatment.

An AE can therefore be any unfavorable and unintended sign (including a clinically significant abnormal laboratory finding, for example), symptom, or disease temporally associated with the use of a medicinal product (investigational or marketed), whether or not considered related to treatment with the medicinal product.

An AE includes:

- An exacerbation of a pre-existing illness, sign, symptom, or clinically significant (as determined by the investigator) laboratory test abnormality and clinically significant ECG abnormality
- An illness, sign, symptom, or clinically significant laboratory abnormality that is detected or diagnosed after study drug administration
- Pretreatment or post-treatment events that occur as a result of protocol-mandated procedures

An AE does not include:

- The disease or disorder being studied or signs and symptoms associated with the disease or disorder, unless there is worsening of the condition of the disease or disorder
- A pre-existing disease or condition, present at the start of the study, that does not worsen

## Overdose

Defined as an accidental or intentional administration of an excessive dose of a product, an overdose should be reported to the sponsor using the SAE form. This information will be shared with the NPS Safety Management Team (SMT) and the sponsor's medical monitor.

### 6.2.1.2 Procedures for Reporting Adverse Events

Adverse events may be spontaneously reported by the subject, obtained through nonleading questioning, or noted during examination of a subject. Adverse events will be recorded from the signing of the ICF through the last dose of study drug. Adverse events that are not resolved at the end of study will be monitored with a telephone call by the investigator, as necessary, for approximately 4 weeks after the last dose of study drug or until resolution or until the AE is judged by the investigator to have stabilized.

As they occur, new AEs will be recorded sequentially on the AE page of the CRF. The AE term should note the diagnosis whenever possible, not the individual signs or symptoms (eg, myocardial infarction should be recorded rather than chest pain, elevated cardiac enzymes, and abnormal ECG). Also recorded are:

- Start and stop date and time (date the site becomes aware of the SAE)
- Whether the event is continuing
- Frequency (intermittent, continuous)
- Intensity (mild, moderate, severe)
  - Mild: usually transient, requiring no special treatment and generally not interfering with usual daily activities
  - Moderate: usually ameliorated by simple therapeutic maneuvers and impairs usual activities
  - Severe: requires vigorous therapeutic intervention and interrupts usual activities. Hospitalization may or may not be required.
- Relationship to study drug (not related, related): identify relationship as “related” if a causal relationship between the investigational product and an AE is at least a reasonable possibility
- Whether the AE is serious (ie, an SAE). If identified as an SAE, the AE should be reported on the SAE form according to Section [6.2.2](#) below
- Actions taken (none; study drug dose changed, interrupted, or discontinued; other medication change; nondrug therapy)
- Outcome (resolved, resolved with sequelae, ongoing, fatal). An individual AE receives only one outcome.

Adverse events that are related to study drug and not resolved at the end of treatment will be followed by the site until resolution or until the AE is judged by the investigator to have stabilized.

Laboratory values, blood pressure, ECG evaluations, and clinical findings at the scheduled physical examinations must be reported as AEs if they:

- Are considered clinically significant by the investigator (ie, not part of the subject's medical history),
- Fulfill SAE criteria, and/or
- Cause subject discontinuation from the study.

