## **6.2.2 Serious Adverse Events**

An SAE must be recorded on the SAE Form. An SAE requires expeditious handling to comply with regulatory requirements. Any SAEs occurring from the signing of the ICF through 30 days after the last dose of study drug will be captured and must be reported within 24 hours after the investigator is made aware of the event.

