### **6.2.2.2 Procedures for Reporting Serious Adverse Events**

Within 24 hours of becoming aware of ANY SAE (regardless of its relationship to investigational product) that occurs during the course of the clinical study from the time the subject signs the ICF through 30 days after the study drug is completed, the investigator must enter the SAE information into the SAE reporting system and fax supplemental data (eg, medical records or laboratory values, if applicable) to the sponsor. This ensures timely reporting of applicable reports to Health Authorities.

Note: Minimum criteria for reporting an SAE are the SAE term, an identifiable subject, a suspect investigational medical product (study drug), and a reporter. Hospitalization is not an AE, but an SAE criterion. The SAE term is the medical event that led to the hospitalization. Surgery is not an AE, but the event that required the subject to have surgery is the SAE term. Death is not an SAE, but an outcome.

The sponsor or designee will provide a FAX cover sheet for the investigators in the study reference manual.

Autopsy reports, if applicable, will be forwarded as they become available. All pertinent laboratory results should be entered on the SAE form.

All SAEs must be reported, whether or not they are considered causally related to the study drug. Appropriate clinical, diagnostic, and laboratory measures should be performed to delineate the cause of the SAE in question and the results reported. Follow-up for the SAE should occur at appropriate intervals until the event/laboratory abnormality:

- Returns to baseline or
- Becomes stable to a clinically acceptable level that is safe for the subject.

The investigator is required to assess the causal relationship of each reported SAE, to the study drug (see below). A causality assessment should always be included on the SAE form. The

investigator should make the causality assessment based on the information available at the time of the event. The causality can be updated at a future date if additional information is received.

The causality categories are:

Not related

- May or may not follow a reasonable temporal sequence from administration of the study product
- Is biologically implausible and does not follow a known response pattern to the suspect study product (if response pattern is previously known)
- Can be explained by the known characteristics of the subject's clinical state or other modes of therapy administered to the subject

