**Table 6-2 Schedule of Evaluations and Procedures – Stage 2**

( X ) = Possible PK sampling time point (Refer to footnote “i”); [ X ] = Possible interim safety evaluation time point (Refer to footnotes “f” and “g”);  
BMI = body mass index; 48-hour I/O = 48-hour fluid intake/urine output; ECG = electrocardiogram; PK = pharmacokinetic; PN = parenteral nutrition;  
PN/I.V. = parenteral nutrition/intravenous (volume); V = visit

a Subject does not have to visit the clinic for visit. Assessments will be completed over the phone.

b Subjects with an early termination visit should have all applicable Visit 10 assessments. Call sponsor for guidance.

c A full physical examination is to be performed at baseline and Visit 10; a brief examination will be performed at all other dosing weeks with a clinic visit.

d The PN/I.V. evaluation is to confirm weekly volume for Inclusion Criteria 5 (PN/I.V. frequency) and 6 (stable PN/I.V.).

e This is the second of 2 body weight measurements that will be used to determine drug volume.

f Interim safety evaluations will be performed 5 to 7 days after any scheduled visit when a reduction has been made to the subject’s PN/I.V. These measures include 48-hour oral fluid intake, 48-hour urine output, hematocrit, serum blood urea nitrogen and creatinine, and urine sodium.

g At the Visit 4/Week 2 interim safety visit, laboratory evaluations and 48-hour I/O are not required. These will be assessed only if the PN/I.V. adjustment was tolerated.

h All subjects will measure 48-hour oral fluid intake and urine output at home immediately prior to the scheduled visit. The measurements should include 1 day on and 1 day off PN/I.V., unless PN is infused daily.

i Samples for PK analysis are collected pre-dose, at 15, 30 and 60 minutes post-dose and at 2, 3, 4, 6, 8, 10 and 12 hours post-dose. If PK sample collection is missed at Visit 2, PK sample may be collected at any visit through Visit 7.

j Subjects will be trained to self-inject teduglutide at baseline on Day 0 (Visit 2). The first injection should be administered under the supervision of the investigator or designee and the subject observed for at least 4 hours. Subjects will self-inject the study drug at home.

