### 8.3.1 Statistical Methods for Safety Variables

Adverse events will be coded using the most recent version of the MedDRA dictionary. Treatment-emergent AEs will be summarized by system organ class and preferred term using descriptive statistics (eg., number and percentage of subjects) for each treatment group. Adverse events will be summarized by severity, relationship to treatment, AEs leading to discontinuation, and AEs leading to death. SAEs will also be tabulated by overall and treatment-related events.

For laboratory tests, 48-hour urine output, vital signs, body weight, BMI, and ECG variables, descriptive statistics (eg, n, mean, standard deviation, median, minimum and maximum values, the number and percentage of subjects in specified categories) will be used to summarize the absolute values and change from Baseline at each time point for each treatment group.

The number and percentage of subjects classified as having antibodies to teduglutide will be used to summarize the presence of antibodies for each treatment group.

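### Section 6.2.1.2 merges the site's SAE awareness date with the event's start and stop dates, so SAE onset can be recorded wrongly

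*Protocol*

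**What the plan says.** Section 6.2.1.2 sets the recording period for adverse events: "Adverse events will be recorded from the signing of the ICF through the last dose of study drug". Pre-dose and on-treatment events therefore go into the same records. They are entered as follows: "As they occur, new AEs will be recorded sequentially on the AE page of the CRF". The list of recorded items has one date entry, "Start and stop date and time (date the site becomes aware of the SAE"). The other items cover whether the event continues, frequency, intensity, relationship, seriousness, action taken and outcome. The line is identical in the three full protocol versions in the file.

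The SAE sections use two clocks. Section 6.2.2 sets the capture window by when the event happens: "Any SAEs occurring from the signing of the ICF through 30 days after the last dose of study drug will be captured". It sets the reporting deadline by knowledge of the event, which "must be reported within 24 hours after the investigator is made aware of the event". Section 6.2.2.2 repeats the window for SAEs that occur "from the time the subject signs the ICF through 30 days after the study drug is completed".

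On the analysis side, Section 8.3.1 says "Treatment-emergent AEs will be summarized by system organ class and preferred term". Table 6-2 collects adverse events at Visit 2, which is also the first dosing day: "Subjects will be trained to self-inject teduglutide at baseline on Day 0 (Visit 2").

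**The concern.** Onset and awareness serve different purposes. Onset places an event before or after the first dose, gives its time from first or last dose and, with resolution, its duration. Awareness starts the sponsor's reporting clock. If sites enter awareness in the start field for SAEs, these properties become wrong for the events that matter most, and the true onset cannot be recovered from that field. If some sites read the line one way and some the other, one column holds two quantities and nothing shows which is which.

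The exposed point is Day 0. Adverse events are collected on the day of the first injection, so an SAE from the stabilization period that the site first hears of at that visit would carry the first-dose date.

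**Working it through.** The protocol gives no figure to reproduce. The check compares the sections and then applies simple date logic. The dates in steps 2 to 4 are illustrative assumptions.

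**Notation.** O = true onset, A = date the site becomes aware, R = recorded start date. First dose = Day 0 (Table 6-2). L = last dose. The SAE window closes at L + 30 (Sections 6.2.2 and 6.2.2.2). Under the literal reading, an SAE has R = A, so the error in the start date is A − O. Under the intended meaning, R = O and the error is 0.

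**Step 1. Can the bracket work as a definition?** The item asks for two dates and a time. The bracket supplies one date and no time. If it governed both, start = stop = A, and the recorded duration would be A − A = 0 days whatever the true duration. If it governed only the start, the duration would be shortened by A − O. The bracket therefore fails as a definition. Read instead as a misplaced extra item, it leaves the awareness date without a field of its own.

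**Step 2. Non-serious event, O = Day −10, A = Day 0.** The bracket names SAEs only. R = Day −10, which is before Day 0, so the event stays pre-dose. The only exposure is that the line stands in the list for all adverse events and a site could apply it more widely.

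**Step 3. SAE, O = Day −10, A = Day 0.** Literally, R = Day 0 and the error is 0 − (−10) = 10 days.
- If treatment emergence means a start date on or after the first-dose date, 0 ≥ 0 and the SAE counts as treatment-emergent.
- If the rule uses clock time and the event was mentioned before the injection, it remains pre-dose.
- The protocol text shown does not say which rule applies.

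**Step 4. SAE after treatment, O = L + 20, A = L + 35.** By occurrence, 20 ≤ 30, so the SAE must be captured, with a report due within 24 hours of L + 35. Literally, R = L + 35, and 35 > 30. The record would look out of window only in a data set filtered on the recorded start date. The duty to capture and report does not change.

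**The case against.** The strongest case on the other side is that this is a drafting slip. The item already asks for start and stop dates, and neighbouring items such as outcome and continuation presuppose real ones. The bracket makes no sense as a definition, so a competent site would read it as a request to note the SAE awareness date as well. The CRF or SAE form may already hold separate fields. The sponsor also corrected other text between versions (the stage named for the Crohn's assessment in Section 6.2.8), and the last version in the file stops in its summary, so the line may be gone. All of this is fair and keeps the point small. It does not make the line correct: it is an operative data-collection instruction, and no other item in the list separates the two dates.

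A reader might also infer more than the documents support:

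- **All adverse event dates are awareness dates.** The bracket says SAE.
- **Late-learned SAEs drop out of the 30-day window.** Sections 6.2.2 and 6.2.2.2 key the window to occurrence, so such an SAE must still be captured and reported.
- **Pre-dose events become treatment-emergent.** That depends on a rule the protocol does not state. Such a rule commonly sits in the analysis plan, and its absence here is no finding.
- **The error can be sized from the gaps between scheduled visits.** Those gaps overstate it. There is an interim safety evaluation toward the end of stabilization (Table 6-1), interim visits 5 to 7 days after a PN/I.V. reduction, staff reminders at least 48 hours before visits (Section 6.2.7), and telephone follow-up of unresolved events as needed.
- **One reclassified subject moves an incidence by 1/5 = 20 percentage points.** This is true at the minimum enrolment of 5, but it holds for any single event in so small a study and does not measure this defect.

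**Conclusion.** The point holds for SAE records. Section 6.2.1.2 puts onset, resolution and site awareness into one item, against the distinction that Sections 6.2.2 and 6.2.2.2 draw. Followed literally, each SAE's recorded onset is late by A − O days. An SAE that began before the first dose and was first mentioned on Day 0 could be classed as treatment-emergent, and SAE timing and duration would be wrong.

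This rests on two assumptions: that at least some sites follow the bracket as written, and, for the misclassification, that treatment emergence is decided by calendar date. The documents do not allow an estimate of how many SAEs would be affected. SAE capture and expedited reporting are not impaired. The correction should still be made, because it costs almost nothing and removes a real ambiguity from the safety data.

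**What to change.** In Section 6.2.1.2, replace the date item with: *date (and time, if known) of onset and of resolution of the event*. Move the bracketed text to a separate item that applies to SAEs only: *date the site became aware of the SAE*, used for the 24-hour reporting requirement in Section 6.2.2. Check that the CRF and its completion guidelines match. First confirm whether the last protocol version, which breaks off before this section in the file, still carries the line.

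Cost: one line of protocol text and, if not already present, one CRF field for SAEs. No visit, assessment or analysis changes.

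If SAE records already exist, query their start dates against source documents so that each holds the onset date.

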## **6.2.2 Serious Adverse Events**

An SAE must be recorded on the SAE Form. An SAE requires expeditious handling to comply with regulatory requirements. Any SAEs occurring from the signing of the ICF through 30 days after the last dose of study drug will be captured and must be reported within 24 hours after the investigator is made aware of the event.

### **6.2.2.1 Serious Adverse Event Definition**

An SAE is defined as an AE that results in any of the following outcomes:

- Death
- Is life-threatening. A life-threatening AE is any AE that places the subject – in the investigator's opinion – at immediate risk of death from the reaction as it occurred. It does not include a reaction that, had it occurred in a more serious form, might have caused death.
- Persistent or significant incapacity or substantial disruption of ability to conduct normal life functions
- Hospitalization or prolongation of existing hospitalization
- Congenital anomaly/birth defect
- Important medical events that may not result in death, be life-threatening, or require hospitalization may be considered an SAE when, based upon appropriate medical judgment, they may jeopardize the subject or may require medical or surgical intervention to prevent one of the other outcomes listed in this definition. Examples of such medical events include allergic bronchospasm requiring intensive treatment in an emergency room or at home, blood dyscrasias or convulsions that do not result in hospitalization, or the development of drug dependency or drug abuse.

Scheduled and/or elective hospitalizations occurring under the following circumstances will not be defined as SAEs for this clinical study:

- Planned before entry into the clinical study
- Elective treatment of a condition unrelated to the studied indication or its treatment
- Occur on an emergency, outpatient basis and do not result in admission (unless fulfilling the previous criteria)
- Part of the normal treatment or monitoring of the studied indication and not associated with any deterioration in condition

### **6.2.2.2 Procedures for Reporting Serious Adverse Events**

Within 24 hours of becoming aware of ANY SAE (regardless of its relationship to investigational product) that occurs during the course of the clinical study from the time the subject signs the ICF through 30 days after the study drug is completed, the investigator must enter the SAE information into the SAE reporting system and fax supplemental data (eg, medical records or laboratory values, if applicable) to the sponsor. This ensures timely reporting of applicable reports to Health Authorities.

Note: Minimum criteria for reporting an SAE are the SAE term, an identifiable subject, a suspect investigational medical product (study drug), and a reporter. Hospitalization is not an AE, but an SAE criterion. The SAE term is the medical event that led to the hospitalization. Surgery is not an AE, but the event that required the subject to have surgery is the SAE term. Death is not an SAE, but an outcome.

The sponsor or designee will provide a FAX cover sheet for the investigators in the study reference manual.

Autopsy reports, if applicable, will be forwarded as they become available. All pertinent laboratory results should be entered on the SAE form.

All SAEs must be reported, whether or not they are considered causally related to the study drug. Appropriate clinical, diagnostic, and laboratory measures should be performed to delineate the cause of the SAE in question and the results reported. Follow-up for the SAE should occur at appropriate intervals until the event/laboratory abnormality:

- Returns to baseline or
- Becomes stable to a clinically acceptable level that is safe for the subject.

The investigator is required to assess the causal relationship of each reported SAE, to the study drug (see below). A causality assessment should always be included on the SAE form. The

investigator should make the causality assessment based on the information available at the time of the event. The causality can be updated at a future date if additional information is received.

The causality categories are:

Not related

- May or may not follow a reasonable temporal sequence from administration of the study product
- Is biologically implausible and does not follow a known response pattern to the suspect study product (if response pattern is previously known)
- Can be explained by the known characteristics of the subject's clinical state or other modes of therapy administered to the subject

Related (Possibly Related/Probably Related/Related)

- A single occurrence of an event that is uncommon and known to be strongly associated with drug exposure (eg, angioedema, hepatic injury, Stevens-Johnson Syndrome)
- Follows a reasonable temporal sequence from administration of the study product
- May follow a known response pattern to the study product (if response pattern is previously known)
- Could not be reasonably explained by the known characteristics of the subject's clinical state or other modes of therapy administered to the subject, if applicable
- Recurs upon rechallenge after withholding and then reintroducing study product

Contact information for SAE reporting and emergency contact details can be found at the beginning of the protocol and in the study reference manual.

As required by ICH guidelines and global health authorities, the sponsor or designee will notify investigators of all adverse drug reactions that are serious, unexpected, and deemed by the reporting investigator or sponsor to be related to study drug (suspected, unexpected, serious, adverse reaction [SUSAR]). Causality, while assessed, does not negate reporting requirements to the sponsor. An AE, whether serious or not serious, is designated unexpected (unlabeled) if it is not reported in the clinical safety section of the Investigator Brochure (IB) or if the event is of greater frequency, specificity, or severity than is mentioned in the IB. The investigator will receive a copy of the current valid version of the IB prior to the start of the study; however, the investigator will not be required to assess expectedness, nor should expectedness impact the investigator reporting SAEs within the timeframe herein defined.

Upon receiving such notices, the investigator must review and retain the notice. If it is determined that there is an unanticipated signal, the NPS SMT will analyze the data and prepare a summary supporting the determination and interpretation of the findings. The sponsor or designee will send this summary to the investigators with instructions to provide it to their Institutional Review Board (IRB).

The investigator should also comply with the IRB procedures for reporting any other safety information (ie, autopsy reports).

NPS Pharmaceuticals, Inc. or its designee will be responsible for submitting SUSAR reports to the appropriate health authorities. These reports will be submitted within the expedited timeframe.

